6.14.3.12. Malignancy

Treatment-emergent malignancy will be considered an AESI. The counts and percentages of participants with treatment emergent malignancy will be summarized by treatment and PT with decreasing order. Detailed searching criteria can be found in [Appendix 3](#).

6.14.3.13. Metabolic Acidosis

This section is applicable for participants developing T2DM during the study treatment (up to primary database lock [72 weeks] and final database lock [176 weeks]).

Severe/serious treatment-emergent metabolic acidosis, including diabetic ketoacidosis will be captured as an AESI.

The counts and percentages of participants with metabolic acidosis, including diabetic ketoacidosis may be summarized by treatment based on searching criteria in [Appendix 3](#).

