5.1. Inclusion Criteria

Participants are eligible to be included in the study only if all of the following criteria apply:

Type of Participant and Disease Characteristics

1. Have a BMI
 - ≥ 30 kg/m² or
 - ≥ 27 kg/m² and previously diagnosed with at least one of the following weight related comorbidities:
 - hypertension: treated or with systolic blood pressure (SBP) ≥ 130 mmHg or diastolic blood pressure ≥ 80 mmHg
 - dyslipidemia: treated or with low-density lipoprotein (LDL) ≥ 160 mg/dL (4.1 mmol/L) or triglycerides ≥ 150 mg/dL (1.7 mmol/L), or high-density lipoprotein (HDL) < 40 mg/dL (1.0 mmol/L) for men or HDL < 50 mg/dL (1.3 mmol/L) for women
 - obstructive sleep apnea
 - cardiovascular disease (for example, ischemic cardiovascular disease, New York Heart Association (NYHA) Functional Class I-III heart failure)
2. Have a history of at least one self-reported unsuccessful dietary effort to lose body weight
3. In the investigator's opinion, are well-motivated, capable, and willing to
 - learn how to self-inject study drug, as required for this protocol (visually impaired persons who are not able to perform the injections must have the assistance of a sighted individual trained to inject study drug; persons with physical limitations who are not able to perform the injections must have the assistance of an individual trained to inject study drug)
 - inject study drug (or receive an injection from a trained individual if visually impaired or with physical limitations)
 - follow study procedures for the duration of the study, including, but not limited to: follow lifestyle advice (for example, dietary restrictions and exercise plan), maintain a study diary, and complete required questionnaires

Participant Characteristics

4. Are 18 years or older

a. male participants:

- Male participants with partners of childbearing potential should be willing to use reliable contraceptive methods throughout the study and for 5 half-lives of study drug plus 90 days, corresponding to 4 months after the last injection.

b. female participants:

- Female participants not of childbearing potential may participate and include those who are:
 - infertile due to surgical sterilization (hysterectomy, bilateral oophorectomy or tubal ligation), congenital anomaly such as Mullerian agenesis
 - postmenopausal, defined as either

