5.2. Exclusion Criteria

Participants are excluded from the study if any of the following criteria apply:

Medical Conditions***Diabetes-related***

6. Have type 1 diabetes mellitus (T1DM) or T2DM, history of ketoacidosis, or hyperosmolar state/coma
7. Have laboratory evidence diagnostic of diabetes mellitus during screening, including 1 or more of: HbA1c $\geq 6.5\%$ (≥ 48 mmol/mol), FG ≥ 126 mg/dL (≥ 7.0 mmol/L), random glucose or 2-hour glucose measurement from a 2-hour OGTT ≥ 200 mg/dL (≥ 11.1 mmol/L)

Obesity-related

8. Have a self-reported change in body weight >5 kg within 3 months prior to screening
9. Have a prior or planned surgical treatment for obesity (excluding liposuction or abdominoplasty if performed >1 year prior to screening)
10. Have or plan to have endoscopic and/or device-based therapy for obesity or have had device removal within the last 6 months (for example, mucosal ablation, gastric artery embolization, intragastric balloon and duodenal-jejunal bypass sleeve)

Other medical

11. Have renal impairment measured as estimated glomerular filtration rate (eGFR) <30 mL/min/1.73 m², calculated by Chronic Kidney Disease-Epidemiology as determined by central laboratory during screening
12. Have a known clinically significant gastric emptying abnormality (for example, severe diabetic gastroparesis or gastric outlet obstruction) or chronically take drugs that directly affect GI motility
13. Have had a history of chronic or acute pancreatitis
14. Have thyroid-stimulating hormone (TSH) outside of the range of 0.4 to 6.0 mIU/L at screening visit

Note: Patients receiving treatment for hypothyroidism may be included, provided their thyroid hormone replacement dose has been stable for at least 3 months.

Note: TSH values above the normal range can, in some patients, suggest subclinical hypothyroidism. If, in the investigator's opinion, the participant has subclinical hypothyroidism and may require initiation of thyroid hormone replacement during the course of the study, the patient should be excluded from the study.

15. Have obesity induced by other endocrinologic disorders (for example, Cushing Syndrome) or diagnosed monogenetic or syndromic forms of obesity (for example, Melanocortin 4 Receptor deficiency or Prader Willi Syndrome)

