9.2. Sample Size Determination

Approximately 3429 participants will be screened to achieve 2400 randomly assigned to study intervention (600 participants per intervention group).

The sample size determination assumes that evaluation of superiority of 10-mg tirzepatide and tirzepatide 15 mg to placebo will be conducted in parallel, each at a 2-sided significance level of 0.025 using a 2-sample t-test. Additionally, a difference of at least 11% mean body weight percentage reduction from randomization at 72 weeks for 10-mg tirzepatide and/or tirzepatide 15 mg compared with placebo, a common SD of 10%, and a dropout rate of 25% are assumed for statistical power calculations. Under the assumptions above, randomizing 2400 participants in a 1:1:1:1 ratio to tirzepatide 5 mg (600), tirzepatide 10 mg (600), tirzepatide 15 mg (600), and placebo (600) provides more than 90% power to demonstrate superiority of tirzepatide 10 mg and/or 15 mg to placebo.

The chosen sample size and randomization ratio also provides >90% power to establish superiority of 10-mg tirzepatide and 15-mg tirzepatide doses to placebo in term of percentage of participants achieving at least 5% body weight reduction at 72 weeks, conducted in parallel using a Fisher's exact test, each at a 2-sided significance level of 0.025, assuming 25% placebo-treated participants and 90% tirzepatide-treated participants achieving the goal and a dropout rate of 25%.

In addition, assuming that approximately 60% of the randomized population will have prediabetes, the study sample size will also provide more than 90% power to demonstrate superiority of tirzepatide (all doses combined) over placebo in terms of delaying the onset of diabetes for participants with prediabetes at study entry. It is based on the following assumptions: 1.6% (corresponding to annual hazard rate of 0.54%) of participants randomized to tirzepatide and 6% of participants randomized to placebo (corresponding to annual hazard rate of

2.1%) will progress to diabetes during the 3-year period; 49% of participants will drop out (corresponding to annual drop-out rate of 22%) during the same period; and the test will be conducted at a 2-sided significance level of 0.05.

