For the Anaphylactic reaction SMQ, each term is classified by scope (Narrow, Broad) and by category (A, B, C, D). All Narrow terms are category A, and all Broad terms are category B, C, or D. In addition to the usual Narrow and Broad searches, the SMQ defines an algorithm to further refine the cases of interest. For Time Period A analysis, the Anaphylactic reaction SMQ algorithm will be included. The algorithm is based upon events that occur within Time Period A. The counts and percentages of participants who experienced a TEAE for the following will be analyzed for each of the 2 time periods:

- any narrow term from any one of the 4 SMQs indicated above (that is, combined search across narrow of all 4 SMQs)
- any narrow scope term within each SMQ, separately (that is, narrow SMQ search). For Time Period A analysis, any term from Anaphylactic reaction SMQ algorithm.

Injection Site Reactions

The ISR AE will be identified using the MedDRA PT in any of the following:

- HLT of Injection site reaction
- HLT of Administration site reaction
- HLT of Infusion Site Reactions

Pancreatitis Events

Determination of investigator-reported events will be through the “Acute pancreatitis” MedDRA SMQ (20000022, narrow scope) and a “Chronic pancreatitis” PT search of the AE database, while adjudication-confirmed pancreatitis are found from adjudication forms.

Malignancy

The malignancy events will be identified using the MedDRA PT contained in Malignant tumours SMQ (20000194) narrow scope or Tumours of unspecified malignancy SMQ (20000195) narrow scope.

Major Depressive Disorder/Suicidal Ideation

AEs will be searched using MedDRA PTs from SMQs narrow scope: 20000037 [Suicide/self-injury] and 20000167 [Depression (excl suicide and self injury)].

Metabolic Acidosis, Including Diabetic Ketoacidosis

Metabolic acidosis including diabetic ketoacidosis will be identified using the following MedDRA PTs:

- Diabetic ketoacidosis
- Ketoacidosis
- Euglycaemic diabetic ketoacidosis
- Ketonuria
- Diabetic ketosis
- Diabetic ketoacidotic hyperglycaemic coma
- Ketosis
- Lactic acidosis
- Urine ketone body present
- Blood ketone body
- Blood ketone body increased
- Urine ketone body, and
- Blood ketone body present.

Supraventricular Arrhythmias and Cardiac Conduction Disorders

The supraventricular arrhythmias and cardiac conduction disorders events will be identified using the MedDRA PT contained in any of the following SMQs:

- 1) Supraventricular Arrhythmias:

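### The metabolic acidosis and amputation/peripheral revascularisation topics cover only participants who develop T2DM on study, a post-randomisation group expected to hold about 1.0% of tirzepatide and 3.6% of placebo participants

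*SAP*

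**What the plan says.** SAP 6.14.3.2 and 6.14.3.13 begin with the same sentence, "This section is applicable for participants developing T2DM during the study treatment", up to the 72-week and 176-week database locks. Within that scope, treatment-emergent amputation/peripheral revascularisation and severe or serious metabolic acidosis are adverse events of special interest (AESIs). By-treatment counts for each are optional. Neither section gives a denominator or says whether events before T2DM onset count.

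SAP Appendix 3 introduces the acidosis search with "Metabolic acidosis including diabetic ketoacidosis will be identified using the following MedDRA PTs" and lists 13 terms, with no T2DM condition. Four name diabetes. The others include lactic acidosis, ketosis, ketonuria and urine ketone body present. The amputation search has two terms.

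The default in SAP 6.14 is the Safety Analysis Set (SS), which is everyone who took at least one dose. Protocol 5.2 excludes people who "Have type 1 diabetes mellitus (T1DM) or T2DM". Delay of T2DM onset is a key secondary hypothesis (Protocol 9.1), planned on "1.6% (corresponding to annual hazard rate of 0.54%) of participants randomized to tirzepatide and 6% of participants randomized to placebo" progressing over three years (Protocol 9.2).

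**The concern.** Nobody belongs to the in-scope group at randomisation. Entry to it depends on an outcome that treatment is expected to change, so its members need not be comparable between arms. They may also start glucose-lowering medication (Protocol 4.1.2.3 and 6.5), which separates them further from the rest of the trial.

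The restriction also fits poorly with the search it governs, because most of the acidosis terms can be coded in someone without diabetes. In a trial that enrols no one with diabetes, the AESI definition then leaves out nearly the whole treated population. A few related events spread over several terms would not be added together for those participants, and an arm difference in the group would be easier to miss.

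**Working it through.** **Inputs (Protocol 9.2).** 600 participants per arm, so 1800 tirzepatide and 600 placebo; "assuming that approximately 60% of the randomized population will have prediabetes"; three-year progression of 1.6% and 6%; 49% dropout over the same period.

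**Reproducing the plan's figures.** Annual hazard = −ln(1 − p)/3:
- tirzepatide: −ln(0.984)/3 = 0.54%
- placebo: −ln(0.94)/3 = 2.06%, stated as 2.1%
- dropout: −ln(0.51)/3 = 22.4%, stated as 22%

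The stated power above 90% for T2DM delay was checked with 1080 against 360 participants at two-sided 0.05. A log-rank simulation with exponential events and dropout over three years (4000 runs) gives 94.1%. The Schoenfeld approximation is lower: 87.3% over three years and 89.7% over 176 weeks. The stated power is reproducible by simulation, and the progression rates can be used as planning values.

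**Participants in scope.** Number = randomised × prediabetes share × progression rate.
- Tirzepatide: 1800 × 0.60 × 0.016 = 17.3; 17.3/1800 = 0.96%; 99.0% outside.
- Placebo: 600 × 0.60 × 0.06 = 21.6; 21.6/600 = 3.6%; 96.4% outside.
- Each tirzepatide dose: 600 × 0.60 × 0.016 = 5.8, about 6 people.

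**Range for the share outside.** The documents give no conversion rate for normoglycaemic participants; the base case takes zero.

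| Assumption | Tirzepatide | Placebo |
|---|---|---|
| Normoglycaemic participants convert at the prediabetes rate | 98.4% | 94.0% |
| Base case | 99.0% | 96.4% |
| Planned dropout over 3 years (12.6 and 15.8 cases) | 99.3% | 97.4% |
| 72 weeks only, constant hazard, no dropout | 99.6% | 98.3% |

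**What the by-arm display would show.** Let every in-scope participant have the same event risk r, so there is no treatment effect on the event. The placebo-to-tirzepatide (pooled) ratio is:
- T2DM cases as denominator: r/r = 1.0
- raw counts: 21.6r/17.3r = 1.25
- all randomised as denominator: 3.6%/0.96% = 3.75

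The SAP does not say which applies. Even at 1.0 the comparison is between groups selected after randomisation, with about 6 people per dose.

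**The case against.** The strongest reply is that little is hidden. For all treated participants, whether or not they develop T2DM, the SAP provides:
- treatment-emergent events by preferred term and system organ class, compared between arms (6.14.1.1);
- serious events in a table and a full listing (6.14.1.4);
- narratives for deaths, serious events and permanent discontinuations due to adverse events (6.14.2);
- shift tables for laboratory analytes with Fisher's exact test (6.14.6), and bicarbonate is in the chemistry panel (Protocol 10.2);
- separate, unrestricted AESIs for severe gastrointestinal, renal and dehydration events.

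The amputation search has only two terms, so the ordinary table shows almost everything a grouped count would. Neither topic is in the AESI list of Protocol 9.4.4.3, the displays are optional, and they test no hypothesis. The SAP aligned its special-topic wording with a program-level safety plan that is not among these documents, so the limit may be a deliberate adaptation for complications of diabetes.

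Most of this stands, and it rules out two stronger readings. A reader might infer that acidosis or amputation events in participants without T2DM go unreported; the tables, listing and narratives above show otherwise. A reader might also infer that placebo would show 3.75 times as many events at equal risk; that needs a denominator the SAP never states.

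The reply does not justify the restriction as the main display. A link to diabetes would support an additional T2DM-only table, but the acidosis search contains terms that do not require diabetes. The general tables also do not add the 13 acidosis terms together.

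**Conclusion.** The point holds at minor-to-moderate severity. Two AESI topics are confined to a post-randomisation subset that the trial expects tirzepatide to shrink. About 99% of tirzepatide participants (range 98.4% to 99.6%) and 96% of placebo participants (range 94.0% to 98.3%) are expected to fall outside. These are planning expectations; they rest on the protocol's progression rates and on the assumption about normoglycaemic conversion.

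The loss is the grouped Appendix 3 search, AESI status and a by-arm comparison in the randomised safety population. It is material mainly for acidosis and slight for amputation/revascularisation. The documents give no rate of these events without diabetes, so the number left out of the grouped counts cannot be estimated. Efficacy results and type 1 error control are unaffected; SAP 6.6 makes no multiplicity adjustment for safety.

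**What to change.** Remove the T2DM restriction from SAP 6.14.3.2 and 6.14.3.13. Run both Appendix 3 searches on the full SS by randomised arm, for the two postbaseline periods in SAP 6.14, with treated participants in the arm as the stated denominator. Flag incident T2DM and its onset date in the listing, so that events before and after onset can be told apart. Keep any T2DM-only display as supplementary, described as non-randomised.

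The cost is a short SAP edit and two tables with listings; no new data are needed. One downside is that non-specific ketone terms enter the grouped acidosis count. Showing each preferred term separately within the group keeps diabetic ketoacidosis distinguishable from ketonuria or ketosis.

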6.14.3.14. Renal Safety

Laboratory measures related to renal safety will be analyzed as specified for laboratory measurements in Section [6.14.6](#).

Two shift tables examining renal function will be created. A min-to-min shift table of estimated glomerular filtration rate (eGFR) estimated by the Chronic Kidney Disease Epidemiology Collaboration (CKD-EPI) equation with units ml/min/1.73m², using categories (<30, ≥30 to <45, ≥45 to <60, ≥60 to <90, and ≥90 mL/min/1.73m²). A max-to-max shift table of urine albumin-to-creatinine ratio (UACR), using the categories UACR <30 mg/g, 30 mg/g ≤ UACR ≤ 300 mg/g, UACR >300 mg/g (respectively, these represent normal, microalbuminuria, and macroalbuminuria).

Mixed model repeated measure analyses for eGFR and UACR will be provided. Log transformation will be performed for UACR.

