Visit*	1	2	3*	4	5	6	7	8	9	10	11	12	13	14	15	16	17	18	19	20	21	99*	ED*	801*
Week of Treatment	-2	-1	0	4	8	12	16	20	24	28	32	36	40	44	48	52	56	60	64	68	72	72		4 wks Post TxP
Allowable Deviation (days)*		±3	±3	±3	+7	±3	+7	±3	±3	±3	±3	+7	±3	±3	±3	±3	±3	±3	±3	±3	±7	±7		±3
Fasting Visit*	X	X	X	X	X	X	X	X	X			X			X			X			X	X	X	X
Telephone Visit										X	X		X	X		X	X		X	X				
2-hour oral glucose tolerance test (includes glucose, insulin, c-peptide at each timepoint)*		X																			X		X	
Chemistry panel (include Cr for eGFR calculation and glucose)*	X		X			X			X			X			X			X			X		X	X
Lipid panel	X		X						X												X		X	X
Fasting insulin						X			X			X			X			X			X		X	X
C-peptide						X			X			X			X			X			X		X	X
Free fatty acids	X		X						X												X		X	X
Urinary albumin/creatinine	X*								X												X		X	X
Cystatin-c	X*								X												X		X	X
Calcitonin	X*					X			X												X		X	X
Hematology	X*					X			X												X		X	X
HbA1c	X		X			X			X			X			X			X			X		X	X
Pancreatic amylase, lipase	X		X			X			X												X		X	X
Thyroid-stimulating hormone	X*																							
Immunogenicity (includes PK sample)*			X	X		X			X						X						X		X	X
TZP PK*					X		X					X												
Pharmacogenetic stored sample			X																					

Visit*	1	2	3*	4	5	6	7	8	9	10	11	12	13	14	15	16	17	18	19	20	21	99*	ED*	801*
Week of Treatment	-2	-1	0	4	8	12	16	20	24	28	32	36	40	44	48	52	56	60	64	68	72	72		4 wks Post TxP
Allowable Deviation (days)*		±3	±3	±3	+7	±3	+7	±3	±3	±3	±3	+7	±3	±3	±3	±3	±3	±3	±3	±3	±7	±7		±3
Fasting Visit*	X	X	X	X	X	X	X	X	X			X			X			X			X	X	X	X
Telephone Visit										X	X		X	X		X	X		X	X				
Nonpharmacogenetic stored sample			X			X			X						X						X		X	X
Mental Health Questionnaires																								
PHQ-9*	X		X			X			X			X			X			X			X	X	X	X
C-SSRS (Baseline/Screening Version)*	X																							
C-SSRS (Since Last Visit Version)*		X	X	X	X	X	X	X	X	X	X	X	X	X	X	X	X	X	X	X	X	X	X	X
Self-Harm Supplement Form*	X	X	X	X	X	X	X	X	X	X	X	X	X	X	X	X	X	X	X	X	X	X	X	X
Self-Harm Follow-up Form*	X	X	X	X	X	X	X	X	X	X	X	X	X	X	X	X	X	X	X	X	X	X	X	X
Patient Reported Outcomes																								
PGIS			X																			X	X	
SF-36, version 2, acute form			X																			X	X	
IWQOL-Lite CT			X																			X	X	
EQ-5D-5L			X																			X	X	

1.3.2. Schedule of Activities for additional 2-year treatment period for participants with prediabetes at randomization

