2-hour oral glucose tolerance test (includes glucose, insulin, c-peptide)	2-hour OGTT testing should be omitted at visits following a protocol-defined diabetes diagnosis.

Urinary albumin/creatinine ratio Cystatin-c Calcitonin Hematology Thyroid-stimulating hormone (TSH)	Screening visit assessment will be used to confirm eligibility. If calcitonin results are not available, a final review of eligibility will occur at Visit 3 before randomization can proceed.
Chemistry panel (include Cr for eGFR calculation)	The CKD-EPI equation will be used by the central lab to estimate and report eGFR.
Immunogenicity (includes PK sample)	PK samples for immunogenicity must be taken prior to drug administration at these visits. In the event of systemic drug hypersensitivity reactions (immediate or nonimmediate), additional blood samples will be collected including ADA, PK, and exploratory biomarker samples.
TZP PK	PK samples will be collected at these visits at time windows of 1 to 24 hours, 24 to 96 hours, or 120 to 168 hours post dose, as assigned by IWRS at randomization. Dependent on the time windows to which a participant is assigned, they may be required to come to site for PK-specific visits.
PHQ-9 C-SSRS (Baseline/Screening Version) C-SSRS (Since last Visit Version) Self-Harm Supplement Form	The C-SSRS, Self-Harm Supplement Form and PHQ-9 should be administered after assessment of adverse events. For this study, the C-SSRS is adapted for the assessment of the ideation and behavior categories only. The Intensity of Ideation and Lethality of Behavior sections are removed.
Self-Harm Follow-up Form	Self-Harm Follow-up Form is only required if triggered by the Self-Harm Supplement Form, per instructions in the form.

Abbreviations: ADA = antidrug antibody; BP = blood pressure; CKD-EPI = Chronic Kidney Disease-Epidemiology; Cr = creatinine; C-SSRS = Columbia-Suicide Severity Rating Scale; ECG = electrocardiogram; ED = early discontinuation of treatment; eGFR = estimated glomerular filtration rate; HR = heart rate; IWRS = interactive web-response system; OGTT = oral glucose tolerance test; PHQ-9 = Patient Health Questionnaire-9; PK = pharmacokinetic; TSH = thyroid-stimulating hormone; TZP = tirzepatide.

2. Introduction

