Abbreviations: ADA = antidrug antibody; ALT = alanine aminotransferase; ALP = alkaline phosphatase; AST = aspartate aminotransferase; BUN = blood urea nitrogen; CK = creatinine kinase, CKD-EPI = Chronic Kidney Disease-Epidemiology; eGFR = estimated glomerular filtration rate; EDTA = ethylenediaminetetraacetic acid; FSH = follicle-stimulating hormone; HbA1c = hemoglobin A1c; HDL = high-density lipoprotein; IWRS = interactive web-response system; LDL = low-density lipoprotein; PK = pharmacokinetics; RBC = red blood cells; TSH = thyroid-stimulating hormone; UACR = urine albumin/creatinine ration; VLDL = very low-density lipoprotein; WBC = white blood cells.

- ^a All tests will be performed by a Lilly-designated central laboratory, unless otherwise noted.
- ^b A serum pregnancy test will be performed at Visit 1 for women of childbearing potential only.

A urine pregnancy test must be performed at Visit 3 with the result available prior to randomization and first injection of study drug(s) for women of childbearing potential only. Additional pregnancy tests (beyond those required per the Schedule of Activities [Section 1.3]) should be performed at any time during the trial if a menstrual period is missed, there is clinical suspicion of pregnancy, or as required by local law or regulation.
- ^c Estimated glomerular filtration rate will be calculated by the central laboratory at all visits and included in lab result reports.
- ^d Follicle-stimulating hormone test performed at Visit 1 for postmenopausal women at least 40 years of age with an intact uterus, not on hormone therapy, and who have had spontaneous amenorrhea for more than 1 year without an alternative medical cause.
- ^e Results will not be provided to the investigative sites.
- ^f PK samples will be collected at these visits at time windows of 1 to 24 hours, 24 to 96 hours, or 120 to 168 hours postdose, as assigned by IWRS. Dependent on the time-windows to which a participant gets assigned, they may be required to come to site for PK-specific visits.
- ^g In the event of systemic drug hypersensitivity reactions (immediate or nonimmediate), additional blood samples will be collected including ADA, PK, and exploratory biomarker samples. PK samples for immunogenicity must be taken prior to drug administration.

Selected tests may be obtained in the event of anaphylaxis or systemic allergic/hypersensitivity reactions.

Hypersensitivity Tests^a

Anti-LY antibodies (immunogenicity)

Tryptase^b

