10.3.1.12. Acute Renal Events

Renal safety will be assessed based on repeated renal functional assessment as well as assessment of AEs suggestive of acute or worsening of chronic renal failure. Gastrointestinal

AEs have been reported with tirzepatide, including nausea, diarrhea, and vomiting. This is consistent with other GLP-1R agonists (Aroda and Ratner 2011). The events may lead to dehydration, which could cause a deterioration in renal function, including acute renal failure. Participants should be advised to notify investigators in case of severe nausea, frequent vomiting, or symptoms of dehydration.

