Appendix 1. Body Composition Assessments via Dual-Energy X-ray Absorptiometry (DXA)

This section is applicable to the participants who are enrolled in the Dual Energy X-ray Absorptiometry (DXA) addendum.

The primary objective of DXA addendum is to demonstrate that tirzepatide (5 mg, 10 mg, and 15 mg combined) QW is superior to placebo in percent change in total body fat mass from baseline to 72 weeks.

Percent change of total body fat mass will be calculated as:

$$\left[\frac{\text{Total body fat mass at 72 weeks} - \text{Total body fat mass at baseline}}{\text{Total body fat mass at baseline}} \right] * 100$$

The secondary objectives include

- To demonstrate that tirzepatide (5 mg, 10 mg, and 15 mg combined) QW is superior to placebo in loss of total body fat mass in kg from randomization to 72 weeks, and
- To assess, for tirzepatide (5 mg, 10 mg, and 15 mg combined) QW, the following parameters, measured at randomization and 72 weeks:
 - Percent change in total body lean mass, and
 - change in total body lean mass in kg.

Percent change of total body lean mass will be calculated as:

$$\left[\frac{\text{Total body lean mass at 72 weeks} - \text{Total body lean mass at baseline}}{\text{Total body lean mass at baseline}} \right] * 100$$

DXA will be performed at the baseline and at the end of 72-week treatment (Visit 21) or ED.

In addition to the primary and secondary outcomes listed above, the following parameters will also be analyzed:

- total body mass (kg)
- total body fat mass (kg)
- total body lean mass (kg)
- percent body fat mass = total body fat mass / total body mass * 100
- percent body lean mass = total body lean mass / total body mass * 100
- fat lean mass ratio = total body fat mass / total body lean mass
- fat lean mass loss ratio = total body fat mass change / total body lean mass change, and
- fat lean mass percent loss ratio = percent change of total body fat mass / percent change of total body lean mass.

Unless otherwise specified, all analyses for the variables measured or derived from DXA will be conducted on all participants who are enrolled in this addendum, randomized, and have at least 1 dose of study drug, with both baseline and at least 1 postbaseline measurement. Baseline is defined as the last non-missing data collected at randomization (prior to first dosing of study drug). Missing data at Week 72 will be imputed using the last observation carried forward method.

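### The planned eGFR analyses rest on serum creatinine alone, so muscle loss accompanying weight loss could mask a modest gradual fall in GFR on tirzepatide; cystatin C is already drawn but no eGFR is derived from it

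*SAP*

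**What the plan says.** SAP 6.14.3.14 (Renal Safety) specifies "A min-to-min shift table of estimated glomerular filtration rate (eGFR) estimated by the Chronic Kidney Disease Epidemiology Collaboration (CKD-EPI) equation", with cut-points at 30, 45, 60 and 90 mL/min/1.73 m2. It adds MMRM analyses of eGFR and UACR and a UACR shift table. It does not say which marker enters the equation.

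The protocol settles that:

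- The Schedule of Activities (1.3.1) lists "Chemistry panel (include Cr for eGFR calculation and glucose", and its notes add "The CKD-EPI equation will be used by the central lab to estimate and report eGFR".
- Appendix 2 (10.2) states "Estimated glomerular filtration rate will be calculated by the central laboratory at all visits and included in lab result reports". That covers chemistry visits at which no cystatin C is drawn (Weeks 0, 12, 36, 48 and 60 in the main period), so the value there can only be creatinine-based.

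Cystatin C is scheduled at Visit 1, Weeks 24 and 72, early discontinuation and Visit 801 (1.3.1), and at Weeks 124 and 176, early discontinuation and Visit 802 (1.3.2). The only purpose given is in the schedule notes, where the screening value sits in a group used for eligibility ("Urinary albumin/creatinine ratio Cystatin-c Calcitonin Hematology"), although no criterion in 5.1 or 5.2 uses it. The SAP never names cystatin C.

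Protocol 10.3.1.12 says "Renal safety will be assessed based on repeated renal functional assessment", together with review of renal adverse events. Protocol 9.2 assumes at least 11 percentage points more weight reduction than placebo at 72 weeks for 10 mg and/or 15 mg. SAP Appendix 1 makes "Percent change in total body lean mass" an outcome in the DXA addendum, without an expected size.

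**The concern.** Creatinine is generated largely by muscle. If participants on tirzepatide lose more muscle than those on placebo, their serum creatinine falls and their creatinine-based eGFR rises at an unchanged true GFR. Randomization does not remove this error, because it arises after baseline and through the treatment effect itself. It runs in one direction: it makes the active arms look better on renal function.

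What is at stake is the reading of the eGFR MMRM and shift table over 72 and 176 weeks. A modest, gradual decline on tirzepatide could appear as no difference from placebo. A marker less dependent on muscle is already being collected, but the plan does not put it on the GFR scale.

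**Working it through.** The documents give no margin, power or bias figure for renal safety, so there is nothing of the plan's own to reproduce. What follows is an illustration on stated assumptions.

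**Step 1. Extra lean loss versus placebo.**
- From the documents: extra weight loss w = 11% (Protocol 9.2).
- Assumed: lean share of the weight lost, s = 15-40%; lean share of body weight, L = 50-60%.
- f = w × s / L.
- Low end: 0.11 × 0.15 / 0.60 = 2.8%. High end: 0.11 × 0.40 / 0.50 = 8.8%. So f is about 3-9%.

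**Step 2. Hidden fall in GFR.**
- Assumed: at steady state, creatinine generation = GFR × serum creatinine, and generation is proportional to lean mass.
- If lean mass falls by f and true GFR falls by d, the creatinine ratio is (1 − f)/(1 − d).
- When d = f the ratio is 1. Creatinine, and hence eGFR, does not move, whatever the slope of the equation.
- At a baseline of 90: 90 × 0.03 = 2.7 and 90 × 0.09 = 8.1 mL/min/1.73 m2.
- At a baseline of 60: 60 × 0.03 = 1.8 and 60 × 0.09 = 5.4.

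**Step 3. What the analysis would show.** Take eGFR proportional to creatinine to the power −b, with b = 1.0 to 1.2 assumed.

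| Lean loss f | Apparent eGFR change, true GFR constant | Apparent eGFR change, true GFR down 10% |
|---|---|---|
| 3% | +3.1% to +3.7% | −7.2% to −8.6% |
| 5% | +5.3% to +6.3% | −5.3% to −6.3% |
| 7.5% | +8.1% to +9.8% | −2.7% to −3.2% |

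If the equation is much flatter (b = 0.33 to 0.41 assumed, for low creatinine), the upward drift is only about 1-4% for lean losses of 3-10%. At 90 that is about 0.9-3.6 mL/min/1.73 m2.

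**Step 4. Compare with what the eGFR comparison can detect.**
- Assumed: SD of eGFR change 8-15; 450 per arm (600 × 0.75, borrowing the 25% dropout in Protocol 9.2); two-sided 0.05; 90% power; simple two-group comparison.
- Detectable difference = SD × (1.960 + 1.282) × √(2/450).
- SD 8 gives 1.73; SD 15 gives 3.24 mL/min/1.73 m2.

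So at a baseline of 90 the hidden fall (2.7-8.1) can match or exceed a difference the model could otherwise find. On the flatter slope the drift (0.9-3.6) overlaps that range less clearly.

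**Step 5. Compare with the shift table.** The closed categories are 15 or 30 mL/min/1.73 m2 wide. The bias is small against that width, so it matters only for participants near a cut-point.

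**The case against.** The strongest case against has four parts.

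**The renal package is wider than eGFR.** This stands as a limit on the point. UACR, acute renal failure and chronic kidney disease searches, and dehydration events are all analysed (SAP 6.14.3.14 to 6.14.3.14.2). None of them corrects the eGFR error, however. UACR measures albuminuria and has urine creatinine in its denominator, and the event searches target clinical events, not slow drift.

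**Cystatin C is probably tabulated already.** A reader might infer that it goes unused. The documents do not support that: 6.14.3.14 sends renal laboratory measures to the generic methods of 6.14.6, and nothing excludes it. A rise by arm could be seen there. But no estimate on the GFR scale or in the <60 and <45 categories results, and MMRM in 6.14.6 is limited to selected tests that are not named.

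**The harm can be overdrawn.** Three stronger readings fail.
- That the trial expects large lean-mass loss: it only plans to measure lean mass, in an addendum subset.
- That acute injury from gastrointestinal fluid loss would be missed: large acute falls would still show in creatinine. Scheduled post-baseline cystatin C starts at Week 24, after the 20-week escalation, so it adds little for that mechanism.
- That at 8% lean loss a true fall from 60 to 54 would escape the <60 category. With an assumed exponent of 1.209, steady-state balance gives 60 × (0.92/0.90)^−1.209 = 58.4, and even simple multiplication gives 54 × 1.106 = 59.7. Either way the participant is counted below 60. The fall fully hidden at 8% is to 55.2.

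**Cystatin C has non-renal influences, including adiposity.** This stands. In a fat-loss trial those influences may also differ by arm, so agreement of the two markers would not prove that there was no decline.

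**Conclusion.** The point holds in limited form. The plan's only GFR estimate is creatinine-based, and the assumed weight effect makes an error that differs by arm and favours tirzepatide plausible. On an assumed 3-9% extra lean loss, a true decline of about 3-9% could be masked.

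The size depends on three things not in the documents: the lean share of the weight lost, proportionality of creatinine generation to lean mass, and steady state. The comparison with a detectable difference also depends on the assumed SD and equation slope. What the documents do establish is the marker, the visit schedule, the 11-point weight assumption and the absence of any cystatin C eGFR.

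This is a minor gap in a safety analysis. It does not affect efficacy, and it does not mean that renal safety goes unassessed.

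**What to change.** In SAP 6.14.3.14:

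1. State that the planned eGFR is creatinine-based CKD-EPI, and name cystatin C among the renal measures.
2. Prespecify, as a supportive analysis, the eGFR shift table and change-from-baseline analysis using CKD-EPI cystatin C eGFR (or the combined creatinine-cystatin C equation) at the visits where cystatin C is drawn.
3. Show creatinine eGFR restricted to those same visits beside it, with the Visit 1 value as baseline for both, so that a difference between markers is not a difference in timing.
4. Report the discordance between the two by arm and interpret it. Do not make the renal conclusion conditional on their agreement.

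The cost is SAP wording, one derived variable and a few tables, with no new sample or visit. SAP 6.2 already leaves room for further analyses, but prespecifying this one keeps the choice of marker from depending on the results.

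The downsides are fewer time points than creatinine, none scheduled after baseline before Week 24 (apart from an earlier early-discontinuation or follow-up visit), and a second marker with its own non-renal influences, including adiposity, which may also differ by arm.
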